5.2.2. Supply of Medications

Sponsor supplies participating sites with Edoxaban, consisting of 60 mg and 30 mg film-coated tablets. The Sponsor will also supply transition kits containing Edoxaban 30 mg and 15 mg to be used for subjects transitioning from Edoxaban to VKA.

Sites or treating physicians will provide or prescribe VKA, clopidogrel, and ASA as per local standard of care guidelines and as specified in the protocol. Please refer to the locally approved label for the summary of product characteristics (SmPC) of each study medication and co-administered medication.

All dosage adjustments for Edoxaban are implemented through the IXRS system at the time of the subject's study visits. For subjects randomized to Edoxaban treatment, the IXRS system provides the appropriate Edoxaban supply kit number based on the subject's information as provided by the Investigator.

5.2.3. cLabeling and Packaging

Edoxaban (DU-176b) will be supplied as tablets (60 mg and 30 mg strengths) packaged in bottles of 60 tablets in each bottle. Two bottles will be supplied to cover the 3 month treatment periods and 4 bottles for the 6 month treatment periods. Edoxaban (DU-176b) will be supplied as 15 mg tablets for end of treatment transition at end of treatment. The transition supply will consist of Edoxaban 30 mg tablets or 15 mg tablets packaged in bottles of 15 tablets each. Protocol-specific packaging and labeling will be completed following Good Manufacturing Principles (GMP).

Subjects will obtain their standard of care medications (e.g., VKA, clopidogrel, and ASA), excluding Edoxaban, either from the site or via prescription from the hospital or treating physician.

5.2.4. Preparation

There is no special preparation for either Edoxaban tablets or VKA.

5.2.5. Administration

For Edoxaban will be dosed as per IXRS. VKA administration will be based on locally approved label instructions. For subjects on VKA, VKA administration should be at doses that will to obtain/maintain an INR of 2.0 to 3.0 (numbers inclusive) [Japan: 1.6 to 2.6 in subjects aged ≥ 70 (numbers inclusive)].

5.2.6. Storage

Edoxaban tablets must be stored by the site at 20° to 25°C (68° to 77°F) as measured by a thermometer in a secure, limited access storage area. Temperature measurements will be recorded on a temperature log excluding weekends and holidays.

Excursions from 15° to 30°C (59° to 86°F) are permitted. The Sponsor/contract research organization (CRO) must be contacted in the event of a temperature excursion outside this range.

Other medications must be stored as per labeled storage conditions.

Upon receipt of shipment, the Investigator or designee will check the amount and condition of the drug, check for appropriate local language in the label, drug expiration date, confirm temperature monitor readings, and sign the Receipt of Shipment Form provided and file the latter in the site binder. The Investigator or designee will contact the IXRS to acknowledge receipt of shipment. In addition, the Investigator or designee shall contact Sponsor/CRO as soon as possible if there is a problem with the shipment and quarantine the shipment until resolution is obtained from the Sponsor.

5.2.7. Edoxaban Accountability

The IXRS will contain a Drug Accountability Module for any medications provided by the Sponsor (i.e., Edoxaban). The Investigator or designee will enter the required information (see IXRS Quick Reference Manual) in the IXRS drug accountability module. In addition, the Investigator or designee shall contact Sponsor as soon as possible if there is a problem with the shipment. A drug accountability record will be provided for Edoxaban. The record must be kept current and should contain the dates and quantities of Edoxaban received, subject's identification number or supply number as applicable, for whom the Edoxaban was dispensed, the date and quantity of Edoxaban dispensed and remaining, as well as the initials of the dispenser.

At the end of the study or as directed, all Edoxaban, including unused, partially used, or empty bottles, will be returned to the Sponsor, a designee, or destroyed at the site according to the site's drug handling and disposition standard operating procedures (SOPs). A copy of these SOPs must be available onsite. The certificate of destruction must be provided to Daiichi Sankyo documenting the drug, the quantity (in tablets), method of destruction, and date of destruction.

If sites are unable to destroy drug, the monitor will make arrangements to return drug to a designated depot for destruction.

Medications provided by the Sponsor will be destroyed (or returned) only after the study monitor has completed an inventory to verify the quantity to be destroyed (or returned). The destruction (or return) of medications provided by the Sponsor must be documented and the documentation filed (and if returned, included in the shipment).

All investigational product inventory forms must be made available for inspection by a Sponsor authorized representative or designee and regulatory agency inspectors. The Investigator is responsible for the accountability of all used and unused study supplies at the site.

5.3. Control Treatment

Sites and or treating physicians will provide or prescribe VKA, clopidogrel, and ASA as per local standard of care guidelines and as specified within the protocol.

5.4. Dose Reductions

Dose reduction for Edoxaban or VKA will be based on the country-specific approved label precautions and recommendations.

5.5. Method of Assessing Treatment Compliance

The first dose of randomized study medication regimen is administered under nursing supervision. Each subject should document missed doses and Investigator captures information in the eCRF.

As per [Table 17.1](#), the Investigator or designee assesses the subject's compliance with the assigned regimen which may include the subject's memory aid; however, dosing compliance will be primarily by:

- Dosing compliance for **Edoxaban** will be assessed by means of tablet/bottle counts remaining or bottles returned. All Edoxaban packaging will be returned at each subject visit; an accounting of tablets will be made and recorded in the eCRF. If zero tablets/bottles returned, ask subject whether any were disposed/thrown away, rather than taken orally, and this information will be recorded in the eCRF.
- Dosing compliance for **VKA** will be assessed by time within the therapeutic range of an INR from 2.0 to 3.0 (numbers inclusive) [Japan: 1.6 to 2.6 in subjects aged ≥ 70 (numbers inclusive)]. INR values will be entered into the eCRF.
- Dosing compliance to any other co-administered medications, (i.e., **oral antiplatelets**) will also be assessed by following prescriptions and subject interview. The information will be recorded in the eCRF.

All information on compliance with medications will be entered into the eCRF.

5.6. Prior and Concomitant Medications

Pre-specified medications that the subject has taken within 30 days before randomization will be recorded in the "targeted concomitant medications" eCRF. Subjects who were or are being treated with oral and/or parenteral anticoagulants are eligible for the study only if from the time of randomization these drugs can be replaced by another oral anticoagulant. These pre-specified medications taken by the subjects upon entry to the study or at any time during the study are regarded as targeted concomitant medications and must be documented on the appropriate pages of the eCRF. If the subject experiences an endpoint event or an SAE, then information on targeted and non-targeted concomitant medications taken within the past 30 days prior to the SAE through to the resolution of the SAE must be documented on the appropriate eCRF pages. Concomitant therapy will be captured through the subject's Post-treatment Follow-up Visit, or in the

case of an SAE reported between that visit and the end of the study, see previous sentence.

With the exception of where the Investigator has pre-declared antiplatelet therapy, there are no other concomitant medications required as part of the study design.

5.7. Prohibited Medications

The following drugs and devices MUST NOT be used during the treatment period unless no alternative therapy is clinically suitable.

- Anticoagulants, other than the assigned study medication, by any route with the exception of parenteral agents used as a bridge when starting or resuming study drug as per approved local label for subject's study drug;
- Fibrinolytic agents, if required to treat acute MI or pulmonary embolism (PE), require study medication interruption and consideration of a transfusion of fresh frozen plasma;
- Dual antiplatelet therapy is prohibited while on study medication except for rare occasions such as for 3 months post coronary stenting (Section 3.1, post TAVI stenting). Examples of dual antiplatelet therapy include aspirin plus a P2Y₁₂ antagonist such as clopidogrel. Single antiplatelet therapy with any antiplatelet agent is permitted as described throughout this protocol.
- Chronic use of NSAIDs including both cyclooxygenase-1 (COX-1) and cyclooxygenase-2 (COX-2) inhibitors other than aspirin for >4 days/week;
- The use of P-glycoprotein (P-gp) inhibitors during this study shall be in accordance with the approved local label for the subject's study medication except as listed below.
 - Systemic use of P-gp inhibitors such as ketoconazole, itraconazole, erythromycin, and clarithromycin may require adjustment of study medication based on the approved local label for the subject's study medication. P-gp inhibitors are generally prescribed for short-term use (≤ 3 weeks). When required use of P-gp inhibitors necessitates the temporary interruption of study medication, or dose reduction for the study drug Edoxaban, the subject should restart study medication after completing treatment with the P-gp inhibitor. Topical use of these medications is allowed while taking study medication.
- Other investigational drugs or devices.

The Investigator is encouraged to contact CRO medical monitor if he/she would like to discuss concomitant medications for a particular subject.

If a subject can safely stop the prohibited concomitant medication (e.g., two-week course of ketoconazole, etc.), then study medication can and should be resumed according to approved local label (usually the day after the last dose of the prohibited concomitant medication). Regardless of the duration of study medication interruption, once the prohibited concomitant medication is stopped, study medication may be resumed.

Information regarding concomitant medications will be collected with start date, stop date, drug name, dose and dosing regimen.

If required as part of standard of care, a reversal agent may be used in accordance with locally approved label.

5.8. Subject Withdrawal/Discontinuation

The intended duration of the two treatment regimens is up to 36 months. Subjects must stay on the assigned OAC-based regimen as much as possible.

Discontinuation of the assigned regimen is mandatory if the CrCL falls below 15 mL/min on two consecutive occasions or if subject is placed on dialysis. If the Investigator doubts the accuracy of the CrCL value calculated with the Cockcroft-Gault formula (Section 17.7), he/she may consider calculating CrCL using a 24-hour urine collection, for confirmatory purposes. If a subject's CrCL, calculated with either the Cockcroft-Gault formula or 24-hour urine collection, recovers to > 15 mL/min, the subject should resume study regimen in line with the applicable labels.

For subjects with a suspected transient decrease in CrCL < 15 mL/min it is recommended that repeat testing of CrCL occur after corrective action is taken or when the medical condition that caused the worsening renal function resolves. The timing of the repeat testing is at the discretion of the Investigator and will vary depending on the nature of the medical condition (e.g., 1-2 weeks for urinary tract infection or over diuresis vs. several weeks to months for glomerulonephritis).

If other clinical contraindications for any study medication develop (according to the label of the respective drug), the study medication must be discontinued (or dose decreased if applicable). If the contraindication resolves, the respective study medication is restarted. During each interruption of anticoagulant or antiplatelet therapy, subjects are evaluated to determine whether the subject can safely resume the study drug. A post-randomization change in health status that results in the subject meeting one or more of the exclusion criteria should only lead to interruption or discontinuation of the assigned medications if the change in health status implies a contraindication according to the drug labels.

Study medications are permanently discontinued if the subject refuses continuation of any medication in the assigned study regimens.

All subjects are followed through to the termination of the study irrespective of changes in the antithrombotic regimen. Clinical follow-up before the end of the study is only terminated at the explicit documented request of the subject or his/her death.

All study drug start and stop dates are captured in eCRF together with the reason for interruption or discontinuation.

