MI	Myocardial infarction
mITT	Modified intention to treat
MLBCs	Major late bleeding complications
NACE	Net adverse clinical events
NSAID	Nonsteroidal anti-inflammatory drug
OAC	Oral anticoagulant(s)
OAP	Oral antiplatelet
PACT-Q	Perception of Anticoagulant Treatment Questionnaire
PCI	Percutaneous coronary intervention
P-gp	P-glycoprotein
PP	Per protocol
PT	Preferred Term
SAE	Serious Adverse Event
SAF	Safety analysis set
SAP	Statistical Analysis Plan
SAPT	Single antiplatelet therapy
SEE	Systemic embolic event
SmPC	Summary of product characteristics
SOP	Standard operating procedures
STS	Society of Thoracic Surgeons
SUSAR	Suspected Unexpected Serious Adverse Reaction
TAVI	Transcatheter aortic valve implantation
TEAE	Treatment-emergent adverse event
TEE	Transesophageal echocardiography or transesophageal echocardiogram
TEG	Thromboelastography
TIMI	Thrombolysis in Myocardial Infarction
TTE	Transthoracic echocardiography or transthoracic echocardiogram
ULN	Upper limit of normal
VKA	Vitamin K antagonist
WBCT	Whole blood clotting time
WHO	World Health Organization

DEFINITIONS SPECIFIC TO THIS PROTOCOL

Term	Definition for this protocol
Discontinuation	Permanent stoppage of study medication. The subject will not be allowed to restart study medication and should follow the transition procedures outlined in Section 5.2.1.1.2 or Section 5.2.1.2.2.
Interruption	A temporary stoppage of study medication. The subject is allowed to restart the study medication at the discretion of the Investigator.
End of TAVI	The clock for randomization starts with the removal of the sheath with hemostasis
End of Study	As an event driven study, enrollment will be stopped no later than at the attainment of a total of 320 subjects experiencing an adjudicated NACE across the combined treatment arms, and , the study will continue until the last subjects enrolled will have accomplished the minimum treatment duration of at least 6 months plus their Post-treatment Follow-up Visit. This Visit by the last subject enrolled will be defined as the end of the study (or common study end date [CSED]).
Major bleeding	Major bleeding is considered to include life-threatening and fatal bleeding.
Study drugs	Any study medication or prescribed oral antiplatelet (OAP) co-administered medication is defined within this protocol as a study drug.

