5.2.1.1.2. Transition from Edoxaban at EOT

For subjects randomized to the Edoxaban-based regimen that require switching from Edoxaban to another anticoagulant at the scheduled end of treatment (EOT) (or due to a premature Edoxaban discontinuation) the following algorithm should be used:

Table 5.2: Transitioning from Edoxaban at EOT

Switching from Edoxaban		
From	To	Recommendation
Edoxaban	VKA	During the transition from Edoxaban to VKA, continuous adequate anticoagulation should be ensured during any transition to an alternate anticoagulant. Oral option: 
 For subjects currently on a 60 mg once-daily dose, administer an Edoxaban dose of 30 mg once-daily together with an appropriate VKA dose. For subjects currently on a 30 mg dose once-daily (for one or more of the following factors: moderate to severe renal impairment (CrCL = 15 to ≤ 50 mL/min), low body weight, or use with certain

Switching from Edoxaban		
From	To	Recommendation

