		
P-gp inhibitors), administer an Edoxaban dose of 15 mg once-daily together with an appropriate VKA dose. Edoxaban 15 mg once-daily is not indicated as monotherapy, as it may result in decreased efficacy. It is only indicated in the process of switching from Edoxaban 30 mg once-daily to VKA, together with an appropriate VKA dose.
 
Subjects should not take a loading dose of VKA in order to promptly achieve a stable INR of 2.0 to 3.0 (numbers inclusive) [Japan: 1.6-2.6 in subjects aged ≥ 70 (numbers inclusive)]. It is recommended to take into account the maintenance dose of VKA if the subject was previously taking a VKA or to use valid INR driven VKA treatment algorithm, in accordance with local practice.
 
Once an INR ≥ 2.0 is achieved [Japan: ≥ 1.6 in subjects aged ≥ 70], Edoxaban should be discontinued. Most subjects (85%) should be able to achieve an INR ≥ 2.0 [Japan: 1.6 in subjects aged ≥ 70 (numbers inclusive)] within 14 days of concomitant administration of Edoxaban and VKA. After 14 days it is recommended that Edoxaban is discontinued and the VKA continued to be titrated to achieve an INR of 2.0-3.0 (numbers inclusive) [Japan: 1.6-2.6 in subjects aged ≥ 70 (numbers inclusive)]. It is recommended that during the first 14 days of concomitant therapy the INR is measured at least three times just prior to taking the daily dose of Edoxaban to minimize the influence of Edoxaban on INR measurements. Concomitant Edoxaban and VKA can increase the INR post Edoxaban dose by up to 46%.
 
Parenteral option: Discontinue Edoxaban and administer a parenteral anticoagulant and VKA at the time of the next scheduled Edoxaban dose. Once a stable INR of ≥ 2.0 is achieved [Japan: ≥ 1.6 in subjects aged ≥ 70], the parenteral anticoagulant should be discontinued and the VKA continued.

Edoxaban	Other non-VKA OAC drugs	Discontinue Edoxaban and start the non-VKA anticoagulant at the time of the next scheduled dose of Edoxaban.
Edoxaban	Parenteral anticoagulants	These agents should not be administered simultaneously. Discontinue Edoxaban and start the parenteral anticoagulant at the time of the next scheduled dose of Edoxaban.

CrCL = creatinine clearance; INR = international normalized ratio; OAC = Oral anticoagulant(s);
P-gp = P-glycoprotein; VKA = vitamin K antagonist

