6.5.1. Transition from Study Medication to Standard of Care VKA

Before transitioning to open-label VKA, all non-transition kit study supplies must be retrieved from the subject to avoid drug administration errors. For information on transitioning of medication, see Section 5.2.1.

The subjects on Edoxaban will use the Sponsor provided transition kit to transition from Edoxaban to a VKA. The choice of VKA will be made by the Investigator in consultation with the subject's personal physician and per local guidelines. More information on this transition from Edoxaban to open-label VKA is available in

Section 5.2.1. Subjects on VKA may be transitioned to another locally approved VKA following local guidelines.

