Subject's follow-up will be required until the values (transaminases, total bilirubin, and direct bilirubin) return to baseline. All clinically significant hepatic enzyme abnormalities and/or hepatic events must be documented in the eCRF. An adjudication dossier should be submitted for events that led to study drug discontinuation or were reported SAEs, where no alternative etiology has been found after work-up and where causal relationship to study drug cannot be ruled out.

The subject may re-start study medication if considered appropriate by the Investigator.

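### The renal stop in Section 5.8 is called a discontinuation but is written to be reversible, and the transition linked to that term does not exclude further edoxaban below 15 mL/min

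*Combined protocol and SAP*

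**What the plan says.** Section 5.8 sets the renal rule: "Discontinuation of the assigned regimen is mandatory if the CrCL falls below 15 mL/min on two consecutive occasions", or on dialysis. Two sentences later it covers recovery to above 15 mL/min, in which case "the subject should resume study regimen in line with the applicable labels".

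The table of definitions specific to this protocol separates two terms. An *interruption* is temporary, and the investigator may restart. A *discontinuation* is permanent: "The subject will not be allowed to restart study medication and should follow the transition procedures" in 5.2.1.1.2 (edoxaban) or 5.2.1.2.2 (VKA).

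Section 5.2.1.1.2 is not limited to the scheduled end of treatment: "or due to a premature Edoxaban discontinuation) the following algorithm should be used". In Table 5.2 the oral route to VKA gives a reduced edoxaban dose together with VKA until the INR reaches 2.0 (1.6 in Japan for age 70 and over), and adds: "After 14 days it is recommended that Edoxaban is discontinued and the VKA continued to be titrated". On a move to VKA, Section 6.5.1 says: "The subjects on Edoxaban will use the Sponsor provided transition kit".

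**The concern.** A mandatory safety stop should tell a site whether the drug may be given again and what to do in the meantime. Here the section and the glossary answer the first question in opposite ways. A site that follows 5.8 restarts the assigned anticoagulant after renal recovery. A site that follows the definition does not.

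The label also decides what happens next. A discontinuation leads to the end-of-treatment visit, return of supplies, an end-of-treatment entry in IXRS for edoxaban, and a move to non-study anticoagulant (6.5; Table 17.1, notes c, l and m). An interruption triggers none of these, and no way back from the end-of-treatment visit is described.

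For an edoxaban subject the discontinuation route also reaches a transition table that can continue edoxaban beside VKA, at a renal function below the level at which 5.8 requires the regimen to stop.

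**Working it through.** No formula applies. The check sets the provisions side by side. The only figures needed (15 mL/min, 14 days, 15 mg and 30 mg, the INR target) are read directly from the text.

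**Step 1. Can both instructions hold?** Under the definitions, a stop that may be restarted is an interruption, and a discontinuation may not be restarted. Section 5.8 uses the second term and then directs a restart. One of the two has to give way.

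**Step 2. Could the resume sentence cover only a single, unconfirmed low value?** Section 5.8 names no hold after one value. The resume sentence belongs to the paragraph that sets the mandatory rule and carries no such limit. The following paragraph, on suspected transient falls, recommends repeat testing but does not introduce a separate hold. The narrow reading is possible, but nothing in the wording supports it.

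**Step 3. Is it an isolated slip?** No. For other label contraindications, 5.8 says the medication must be discontinued (or its dose decreased) and then: "If the contraindication resolves, the respective study medication is restarted". Section 9.2.1 describes a subject who discontinues for liver enzyme abnormalities and then says: "The subject may re-start study medication if considered appropriate by the Investigator".

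**Step 4. Which term was meant?**

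| Provision | Points to |
|---|---|
| 5.8, resume on renal recovery | interruption |
| 5.8, restart when another contraindication resolves | interruption |
| 5.8.2, contraindications listed among reasons for interruption | interruption |
| 5.8, the word permanently attached only to subject refusal | interruption |
| 5.8.1, renal stop listed under a joint interruption/discontinuation heading | neither |
| 5.8 renal rule, read with the definitions table | discontinuation |

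The weight lies with interruption. Section 5.8.1 also asks for confirmation at least one week later; that is an editorial difference, and nothing here rests on it.

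**Step 5. Where does the discontinuation route lead?** The definition points to 5.2.1.1.2 and so to Table 5.2.

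| Route in Table 5.2 | Edoxaban after the stop | Excludes CrCL < 15 mL/min or dialysis? |
|---|---|---|
| To VKA, oral | 15 mg daily if on 30 mg, 30 mg daily if on 60 mg, with VKA, until the INR target; stop recommended after 14 days | No |
| To VKA, parenteral bridge | None from the next scheduled dose | Not needed |
| To a non-VKA oral anticoagulant | None from the next scheduled dose | Not needed |
| To a parenteral anticoagulant | None from the next scheduled dose | Not needed |

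The only renal range the table names is 15 to 50 mL/min, given as one reason a subject may be on 30 mg. It gives no instruction below 15. Section 6.5.1 has no renal exclusion either.

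**Step 6. Scope.** The restart conflict concerns both arms. The overlap concerns the edoxaban arm only, and only when the destination is VKA by the oral route.

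**The case against.** The strongest reply is that the protocol, read as a whole, already resolves the term. Section 5.8.2 classes contraindications as reasons for interruption. Section 5.8 introduces the next group as other contraindications, so it treats the renal stop as one of the same kind. A specific instruction to resume would normally prevail over a glossary entry, and 5.8.2 tells sites to call the medical monitor when in doubt. This stands as evidence of intent. It also means that opposite handling at different sites is possible but not shown. It does not make the wording right: the mandatory rule still uses the term that forbids what the paragraph goes on to direct.

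On the transition, the reply is that nothing compels the overlap. Table 5.2 has routes without further edoxaban. Section 6.5.1 applies only when the subject moves to VKA. Note l of Table 17.1 leaves the choice of anticoagulant to the physician and ties the transition to the approved label. Section 5.8.2 allows other antithrombotic therapy during an interruption or after a discontinuation. All of this stands, and it makes the problem avoidable. None of these provisions is tied to the renal stop, and whether a given label would bar a short overlap below 15 mL/min cannot be checked from the documents.

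A reader might infer that the on-treatment analysis becomes undefined. It does not. The period from initial dose to final dose plus 30 days uses actual dose dates and includes interruptions, start and stop dates are recorded, and the results for that period are descriptive (11.2, 11.4.1). Whichever action a site takes gives a definite period.

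**Conclusion.** The point holds as a drafting error in a safety rule. Section 5.8 requires a discontinuation and directs a resumption that the protocol's own definition forbids. The same misuse occurs in the contraindication paragraph of 5.8 and in 9.2.1. The transition attached to that term leaves room for further edoxaban below the stopping threshold.

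The size is small and cannot be quantified. The documents give no rate of renal stops or of recovery, so the number of subjects affected is unknown. Fourteen days is a recommended stopping point, not a fixed cap, and edoxaban ends earlier if the INR target is reached.

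Two stronger readings are not supported. The protocol does not require edoxaban below 15 mL/min; it fails to exclude it on one of several routes. Nor is there a threat to the primary hypotheses: these are tested in the ITT set over the overall study period, and Sections 5.8 and 5.8.2 keep subjects in follow-up to the end of the study whatever happens to study medication.

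The conclusion rests on the definitions table governing the term used in 5.8, and on reading the resume sentence without a limit that the text does not state.

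**What to change.** **Section 5.8.** State that the assigned regimen:
- must be interrupted at once if CrCL is below 15 mL/min on two consecutive measurements or dialysis is started;
- may be resumed per label only when CrCL is above 15 mL/min and the subject is off dialysis;
- is discontinued, with the end-of-treatment visit, if dialysis is long-term or recovery is not expected.

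Naming dialysis in the resumption condition matters because the present resume sentence refers to CrCL alone.

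**Contraindication paragraph of 5.8, and 9.2.1.** Use *interrupted* wherever restart is allowed, in line with 5.8.2.

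**Sections 5.2.1.1.2 and 6.5.1.** Add that subjects stopped for CrCL below 15 mL/min or dialysis do not use the oral edoxaban overlap or the transition kit, and that edoxaban stops at once with any replacement anticoagulant chosen per local label.

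If the sponsor does intend a permanent renal stop, delete the resume sentence instead; the addition to 5.2.1.1.2 and 6.5.1 is still needed.

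The cost is wording in four sections at the next amendment and a note to sites. No new procedure or data item is required, because the eCRF already records dates and reasons for interruption and discontinuation.
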